Appendix D. Clinical Laboratory Parameters

Serum Chemistry	Hematology	Other
Sodium	Red blood cell count	NT-proBNP (serum)
Potassium	Hemoglobin	Urine pregnancy test (for female
Chloride	Hematocrit	subjects of childbearing potential)
Bicarbonate/CO2	Platelet count	
Blood urea nitrogen/urea	White blood cell count	
Albumin	Prothrombin	
Alkaline phosphatase	time/International	
Alanine aminotransferase (ALT)	Normalized Ratio	
Aspartate aminotransferase (AST)	CD4 count (for subjects with	
Gamma-glutamyl transferase (GGT)	human immunodeficiency	
Total bilirubin	virus [HIV])	
Indirect bilirubin		
Direct bilirubin		
Creatinine		

NT-proBNP, N-terminal pro-brain natriuretic peptide

Tests by Study Visit

Study Visit	Clinical Labs
Screening	Chemistry, hematology, NT-proBNP, urine pregnancy test (for female subjects of childbearing potential), CD4 count (for subjects with HIV)
Baseline	Chemistry, hematology, NT-proBNP, urine pregnancy test (for female subjects of childbearing potential), and optional pharmacogenomics (genetic/RNA) and biomarker sample
Transition Visit	Chemistry, hematology, NT-proBNP, urine pregnancy test (for female subjects of childbearing potential), and biomarker testing in addition to scheduled testing for that study visit
Week 4	Urine pregnancy test (for female subjects of childbearing potential)
Week 8	Urine pregnancy test (for female subjects of childbearing potential)
Week 12	Urine pregnancy test (for female subjects of childbearing potential)
Week 16/Early Study Withdrawal	Chemistry, hematology, NT-proBNP, urine pregnancy test (for female subjects of childbearing potential), and optional biomarker sample

HIV, human immunodeficiency virus; NT-proBNP, N-terminal pro-brain natriuretic peptide; RNA, ribonucleic acid

Appendix E. AE Bothersome Survey

Investigators will ask subjects about the prostanoid-related effects they experienced using the AE Bothersome Survey. For this study, adverse events of interest include headache, diarrhea, nausea, flushing, jaw pain, extremity pain, and vomiting. Scores will be captured at the time points listed in Table 3-1. The Investigator will begin with Question 1, asking the subject about the AEs listed in the left-most column, and proceed to Question 2 and Question 3 for any AEs experienced by the subject. This questionnaire may be used to guide AE assessment and conversations about AEs that a subject is experiencing. Events captured by the AE Bothersome Survey should only be recorded as an AE and should only be captured as an SAE if the event is unusual with respect to intensity, frequency, or duration as compared with symptoms in the subject's medical history (see section 9.1).

AE Bothersome Survey													
Question 1			Question 2				Question 3						
"Have you experie health problem or side effect in the particle yes of proceed to Question Question 3.)	medicati ast week or no . If	ion ?" yes,	"For this health problem or medication side effect that you experienced, how bothersome has it been for you during the last week using the following scale?" 1 – bothers me a lot 2 – bothers me some 3 – bothers me a little 4 – not at all bothersome			that you experienced, how bothersome been for you during the last week using lowing scale?" there me a lot there me some there me a little "For this health problem or medication side effect that you experienced, ho many days in the week did you experience it?"				e ow ne p	ast		
			(Please circle of Question 3.)	ne numb	er and pi	roceed to	-	eas					7.)
Headache	Yes	No	1	2	3	4	1	2	3	4	5	6	7
Diarrhea	Yes	No	1	2	3	4	1	2	3	4	5	6	7
Nausea	Yes	No	1	2	3	4	1	2	3	4	5	6	7
Flushing	Yes	No	1	2	3	4	1	2	3	4	5	6	7
Jaw pain	Yes	No	1	2	3	4	1	2	3	4	5	6	7
Extremity pain	Yes	No	1	2	3	4	1	2	3	4	5	6	7
Vomiting	Yes	No	1	2	3	4	1	2	3	4	5	6	7

Appendix F. Cockcroft-Gault Equation and Child-Pugh Score

Cockcroft-Gault Equation

 $CrCl (mL/min) = [(140 - age) \times AjBW (kg)] / (SCr [mg/dL] \times 72)$

Note: multiply results by 0.85 for females.

Calculation of adjusted body weight in kg:

AjBW = IBW + 0.4(ABW - IBW)

Calculation of ideal body weight in kg:

Males: IBW = 50 kg + 2.3 kg for each inch over 5 feet

Females: IBW = 45.5 kg + 2.3 kg for each inch over 5 feet

Abbreviations: CrCl – creatinine clearance; AjBW – adjusted body weight; ABW – actual

body weight; IBW - ideal body weight; SCr - serum creatinine

Child-Pugh Score

Danier dan	Points			
Parameter	1	2	3	
Hepatic encephalopathy	None (hepatic encephalopathy is absent)	Stage I to II (mild or suppressed with medication)	Stage III to IV (severe or refractory)	
Ascites	None (ascites is absent)	Mild-moderate (suppressed with medication)	Moderate-severe (refractory)	
Total bilirubin µmol/L (mg/dL)	<34 (<2)	34 to 50 (2 to 3)	>50 (>3)	
Serum albumin (g/dL)	>3.5	2.8 to 3.5	<2.8	
Prothrombin time(s)/ International Normalized Ratio	<4 (<1.7)	4 to 6 (1.71 to 2.20)	>6 (>2.20)	

Class A (mild) = 5 to 6 points

Class B (moderate) = 7 to 9 points

Class C (severe) = 10 to 15 points

Appendix G. Treatment Satisfaction Questionnaire for Medication (TSQM) (Version 1.4)

Instructions: Please take some time to think about your level of satisfaction or dissatisfaction with the medication you are taking in this clinical trial. We are interested in your evaluation of the effectiveness, side effects, and convenience of the medication *over the last two to three weeks, or since you last used it.* For each question, please place a single check mark next to the response that most closely corresponds to your own experiences.

1.	How satisfied or condition?	dissatisfied are you with the ability of the medication to prevent or treat your
		1 Extremely Dissatisfied 2 Very Dissatisfied 3 Dissatisfied 4 Somewhat Satisfied 5 Satisfied 6 Very Satisfied 7 Extremely Satisfied
2.	How satisfied or	dissatisfied are you with the way the medication relieves your symptoms?
		1 Extremely Dissatisfied 2 Very Dissatisfied 3 Dissatisfied 4 Somewhat Satisfied 5 Satisfied 6 Very Satisfied 7 Extremely Satisfied
3.	How satisfied or working?	dissatisfied are you with the amount of time it takes the medication to start
		1 Extremely Dissatisfied 2 Very Dissatisfied 3 Dissatisfied 4 Somewhat Satisfied 5 Satisfied 6 Very Satisfied 7 Extremely Satisfied
4.	As a result of tak	ring this medication, do you experience any side effects at all?
		1 Yes 0 No (if No, then please skip to Question 9)

5.	How bothersome are the side effects of the medication you take to treat your condition?
	 □ 1 Extremely Bothersome □ 2 Very Bothersome □ 3 Somewhat Bothersome □ 4 A Little Bothersome □ 5 Not at All Bothersome
6.	To what extent do the side effects interfere with your physical health and ability to function (ie, strength, energy levels, etc)?
	 □ 1 A Great Deal □ 2 Quite a Bit □ 3 Somewhat □ 4 Minimally □ 5 Not at All
7.	To what extent do the side effects interfere with your mental function (ie, ability to think clearly, stay awake, etc)?
	☐ 1 A Great Deal ☐ 2 Quite a Bit ☐ 3 Somewhat ☐ 4 Minimally ☐ 5 Not at All
8.	To what degree have medication side effects affected your overall satisfaction with the medication?
	☐ 1 A Great Deal ☐ 2 Quite a Bit ☐ 3 Somewhat ☐ 4 Minimally ☐ 5 Not at All
9.	How easy or difficult is it to use the medication in its current form?
	☐ 1 Extremely Difficult ☐ 2 Very Difficult ☐ 3 Difficult ☐ 4 Somewhat Easy ☐ 5 Easy ☐ 6 Very Easy ☐ 7 Extremely Easy
10	. How easy or difficult is it to plan when you will use the medication each time?
	☐ 1 Extremely Difficult ☐ 2 Very Difficult ☐ 3 Difficult ☐ 4 Somewhat Easy ☐ 5 Easy ☐ 6 Very Easy ☐ 7 Extremely Easy

ll. How convenier	it or inconvenient is it to take the medication as instructed?
	1 Extremely Inconvenient 2 Very Inconvenient 3 Inconvenient 4 Somewhat Convenient 5 Convenient 6 Very Convenient 7 Extremely Convenient
12. Overall, how c	onfident are you that taking this medication is a good thing for you?
	1 Not at All Confident 2 A Little Confident 3 Somewhat Confident 4 Very Confident 5 Extremely Confident
13. How certain ar	e you that the good things about your medication outweigh the bad things?
	1 Not at All Certain 2 A Little Certain 3 Somewhat Certain 4 Very Certain 5 Extremely Certain
14. Taking all thin	gs into account, how satisfied or dissatisfied are you with this medication?
	1 Extremely Dissatisfied 2 Very Dissatisfied 3 Dissatisfied 4 Somewhat Satisfied 5 Satisfied 6 Very Satisfied 7 Extremely Satisfied

Appendix H. emPHasis-10 Questionnaire

em PH asis	10	NHS/Hospita	al number:
Name:		Date of birth:	
This questionnaire hypertension (PH) question by placing describes your red	affects your life g a tick over the ent experience	e. Please e ONE Ni of living	answer every UMBER that best with PH
I am not frustrated by my breathlessness	0123	4 5	I am very frustrated by my breathlessness
Being breathless never	0 1 2 3	4 5	Being breathless always interrupts my conversations
I do not need to rest during the day	0 1 2 3	4 5	I always need to rest during
I do not feel exhausted	0 1 2 3	4 5	I always feel exhausted
I have lots of energy	0 1 2 3	4 5	I have no energy at all
When I walk up one flight of — stairs I am not breathless	0 1 2 3	4 5	When I walk up one flight of stairs I am very breathless
I am confident out in public places/crowds despite my PH	0 1 2 3	4 5	I am not confident at all in public places/crowds because of my PH
PH does not control my life	0 1 2 3	4 5	PH completely
I am independent	0 1 2 3	4 5	I am completely dependent
I never feel like a burden	0 1 2 3	4 5	I always feel I ke a burden
-			
pha Ck	Total:		Date: MANCHESTER 1824 The University of Manchester

Appendix I. Transition Schedule Examples

3 Days Duration

3 Days Duration for a 70 kg Subject at a Remodulin Dose of 30 ng/kg/min

Transition Day	Remodulin Dose (ng/kg/min)	Orenitram Dose (mg)
	Day 1 (0-24 hours)	22
Morning	30	0
Afternoon	26	0.625
Evening	22	1.375
	Day 2 (24-48 hours)	
Morning	18	2
Afternoon	14	2.625
Evening	10	3.125
	Day 3 (48-72 hours)	
Morning	6	3.75
Afternoon	3	4.375
Evening	0	5

3 Days Duration for a 40 kg Subject at a Remodulin Dose of 30 ng/kg/min

Transition Day	Remodulin Dose (ng/kg/min)	Orenitram Dose (mg)
	Day 1 (0-24 hours)	
Morning	30	0
Afternoon	26	0.375
Evening	22	0.75
	Day 2 (24-48 hours)	
Morning	18	1.125
Afternoon	14	1.5
Evening	10	2
	Day 3 (48-72 hours)	
Morning	6	2.25
Afternoon	3	2.5
Evening	0	2.875

3 Days Duration for a 120 kg Subject at a Remodulin Dose of 30 ng/kg/min

Transition Day	Remodulin Dose (ng/kg/min)	Orenitram Dose (mg)
	Day 1 (0-24 hours)	
Morning	30	0
Afternoon	26	1.125
Evening	22	2.25
	Day 2 (24-48 hours)	
Morning	18	3.5
Afternoon	14	4.625
Evening	10	5.75
	Day 3 (48-72 hours)	
Morning	6	6.875
Afternoon	3	7.75
Evening	0	8.625

3 Days Duration for a 70 kg Subject at a Remodulin Dose of 20 ng/kg/min

Transition Day	Remodulin Dose (ng/kg/min) Day 1 (0-24 hours)	Orenitram Dose (mg)
Morning	20	0
Afternoon	18	0.125
Evening	15	0.25
	Day 2 (24-48 hours)	
Morning	13	0.375
Afternoon	10	0.5
Evening	8	0.625
	Day 3 (48-72 hours)	
Morning	5	0.75
Afternoon	2	0.875
Evening	0	1

3 Days Duration for a 40 kg Subject at a Remodulin Dose of 20 ng/kg/min

Transition Day	Remodulin Dose (ng/kg/min)	Orenitram Dose (mg)
	Day 1 (0-24 hours)	
Morning	20	0
Afternoon	18	0.25
Evening	15	0.5
	Day 2 (24-48 hours)	
Morning	13	0.625
Afternoon	10	1
Evening	8	1.125
	Day 3 (48-72 hours)	
Morning	5	1.5
Afternoon	2	1.75
Evening	0	2

3 Days Duration for a 120 kg Subject at a Remodulin Dose of 20 ng/kg/min

Transition Day	Remodulin Dose (ng/kg/min)	Orenitram Dose (mg)
	Day 1 (0-24 hours)	
Morning	20	0
Afternoon	18	0.625
Evening	15	1.5
	Day 2 (24-48 hours)	
Morning	13	2
Afternoon	10	2.875
Evening	8	3.5
	Day 3 (48-72 hours)	
Morning	5	4.375
Afternoon	2	5.125
Evening	0	5.75

3 Days Duration for a 70 kg Subject at a Remodulin Dose of 40 ng/kg/min

Transition Day	Remodulin Dose (ng/kg/min) Day 1 (0-24 hours)	Orenitram Dose (mg)
Morning	40	0
Afternoon	35	0.875
Evening	30	1.625
	Day 2 (24-48 hours)	
Morning	25	2.5
Afternoon	20	3.375
Evening	15	4.25
	Day 3 (48-72 hours)	
Morning	10	5
Afternoon	5	5.875
Evening	0	6.75

3 Days Duration for a 40 kg Subject at a Remodulin Dose of 40 ng/kg/min

Transition Day	Remodulin Dose (ng/kg/min) Day 1 (0-24 hours)	Orenitram Dose (mg)
Morning	40	0
Afternoon	35	0.5
Evening	30	1
	Day 2 (24-48 hours)	
Morning	25	1.5
Afternoon	20	1.875
Evening	15	2.375
	Day 3 (48-72 hours)	
Morning	10	2.875
Afternoon	5	3.375
Evening	0	3.875

3 Days Duration for a 120 kg Subject at a Remodulin Dose of 40 ng/kg/min

Transition Day	Remodulin Dose (ng/kg/min)	Orenitram Dose (mg)
*	Day 1 (0-24 hours)	1974 - 1984 Hills
Morning	40	0
Afternoon	35	1.5
Evening	30	2.875
	Day 2 (24-48 hours)	
Morning	25	4.375
Afternoon	20	5.75
Evening	15	7.25
	Day 3 (48-72 hours)	
Morning	10	8.625
Afternoon	5	10
Evening	0	11.5

5 Days Duration
5 Days Duration for a 70 kg Subject at a Remodulin Dose of 30 ng/kg/min

Transition Day	Remodulin Dose (ng/kg/min)	Orenitram Dose (mg)
	Day 1 (0-24 hours)	
Morning	30	0
Afternoon	28	0.375
Evening	26	0.625
	Day 2 (24-48 hours)	
Morning	24	1
Afternoon	22	1.375
Evening	20	1.625
	Day 3 (48-72 hours)	
Morning	17	2.125
Afternoon	14	2.75
Evening	12	3
	Day 4 (72-96 hours)	
Morning	10	3.375
Afternoon	8	3.75
Evening	6	4
	Day 5 (96-120 hours)	
Morning	4	4.375
Afternoon	2	4.75
Evening	0	5

5 Days Duration for a 40 kg Subject at a Remodulin Dose of 30 ng/kg/min

Transition Day	Remodulin Dose (ng/kg/min)	Orenitram Dose (mg)
	Day 1 (0-24 hours)	
Morning	30	0
Afternoon	28	0.25
Evening	26	0.375
	Day 2 (24-48 hours)	
Morning	24	0.625
Afternoon	22	0.75
Evening	20	1
	Day 3 (48-72 hours)	
Morning	17	1.25
Afternoon	14	1.5
Evening	12	1.75
	Day 4 (72-96 hours)	
Morning	10	2
Afternoon	8	2.125
Evening	6	2.25
	Day 5 (96-120 hours)	
Morning	4	2.5
Afternoon	2	2.675
Evening	0	2.875

5 Days Duration for a 120 kg Subject at a Remodulin Dose of 30 ng/kg/min

Transition Day	Remodulin Dose (ng/kg/min)	Orenitram Dose (mg)
	Day 1 (0-24 hours)	
Morning	30	0
Afternoon	28	0.625
Evening	26	1.125
	Day 2 (24-48 hours)	
Morning	24	1.75
Afternoon	22	2.25
Evening	20	2.875
	Day 3 (48-72 hours)	
Morning	17	3.75
Afternoon	14	4.625
Evening	12	5.125
	Day 4 (72-96 hours)	
Morning	10	5.75
Afternoon	8	6.375
Evening	6	6.875
	Day 5 (96-120 hours)	
Morning	4	7.5
Afternoon	2	8
Evening	0	8.625

5 Days Duration for a 70 kg Subject at a Remodulin Dose of 20 ng/kg/min

Transition Day	Remodulin Dose (ng/kg/min)	Orenitram Dose (mg)
	Day 1 (0-24 hours)	
Morning	20	0
Afternoon	18	0.375
Evening	17	0.5
	Day 2 (24-48 hours)	
Morning	16	0.625
Afternoon	14	1
Evening	13	1.125
	Day 3 (48-72 hours)	
Morning	11	1.5
Afternoon	10	1.625
Evening	8	2
	Day 4 (72-96 hours)	
Morning	7	2.125
Afternoon	5	2.5
Evening	4	2.625
	Day 5 (96-120 hours)	
Morning	2	3
Afternoon	1	3.25
Evening	0	3.375

5 Days Duration for a 40 kg Subject at a Remodulin Dose of 20 ng/kg/min

Transition Day	Remodulin Dose (ng/kg/min)	Orenitram Dose (mg)
	Day 1 (0-24 hours)	**************************************
Morning	20	0
Afternoon	18	0.125
Evening	17	0.25
	Day 2 (24-48 hours)	
Morning	16	0.375
Afternoon	14	0.5
Evening	13	0.675
	Day 3 (48-72 hours)	
Morning	11	0.875
Afternoon	10	1
Evening	8	1.125
	Day 4 (72-96 hours)	
Morning	7	1.25
Afternoon	5	1.375
Evening	4	1.5
	Day 5 (96-120 hours)	
Morning	2	1.625
Afternoon	1	1.75
Evening	0	2

5 Days Duration for a 120 kg Subject at a Remodulin Dose of 20 ng/kg/min

Transition Day	Remodulin Dose (ng/kg/min)	Orenitram Dose (mg)
	Day 1 (0-24 hours)	
Morning	20	0
Afternoon	18	0.5
Evening	17	0.875
	Day 2 (24-48 hours)	
Morning	16	1.125
Afternoon	14	1.75
Evening	13	2
	Day 3 (48-72 hours)	
Morning	11	2.5
Afternoon	10	2.875
Evening	8	3.5
	Day 4 (72-96 hours)	
Morning	7	3.75
Afternoon	5	4.375
Evening	4	4.625
	Day 5 (96-120 hours)	
Morning	2	5.125
Afternoon	1	5.5
Evening	0	5.75

5 Days Duration for a 70 kg Subject at a Remodulin Dose of 40 ng/kg/min

Transition Day	Remodulin Dose (ng/kg/min)	Orenitram Dose (mg)
*	Day 1 (0-24 hours)	505 (6510)
Morning	40	0
Afternoon	37	0.5
Evening	34	1
	Day 2 (24-48 hours)	
Morning	31	1.5
Afternoon	28	2
Evening	26	2.375
	Day 3 (48-72 hours)	
Morning	23	2.875
Afternoon	20	3.325
Evening	17	3.875
	Day 4 (72-96 hours)	
Morning	15	4.25
Afternoon	12	4.75
Evening	9	5.25
	Day 5 (96-120 hours)	
Morning	6	5.75
Afternoon	3	6.25
Evening	0	6.75

5 Days Duration for a 40 kg Subject at a Remodulin Dose of 40 ng/kg/min

Transition Day	Remodulin Dose (ng/kg/min)	Orenitram Dose (mg)
	Day 1 (0-24 hours)	
Morning	40	0
Afternoon	37	0.25
Evening	34	0.625
	Day 2 (24-48 hours)	
Morning	31	0.875
Afternoon	28	1.125
Evening	26	1.375
	Day 3 (48-72 hours)	
Morning	23	1.625
Afternoon	20	1.875
Evening	17	2.25
	Day 4 (72-96 hours)	
Morning	15	2.375
Afternoon	12	2.625
Evening	9	3
	Day 5 (96-120 hours)	
Morning	6	3.25
Afternoon	3	3.5
Evening	0	3.875

5 Days Duration for a 120 kg Subject at a Remodulin Dose of 40 ng/kg/min

Transition Day	Remodulin Dose (ng/kg/min)	Orenitram Dose (mg)
	Day 1 (0-24 hours)	
Morning	40	0
Afternoon	37	0.875
Evening	34	1.75
	Day 2 (24-48 hours)	
Morning	31	2.625
Afternoon	28	3.5
Evening	26	4
	Day 3 (48-72 hours)	
Morning	23	4.875
Afternoon	20	5.75
Evening	17	6.625
	Day 4 (72-96 hours)	
Morning	15	7.25
Afternoon	12	8
Evening	9	8.875
	Day 5 (96-120 hours)	
Morning	6	9.75
Afternoon	3	10.625
Evening	0	11.5

9 Days Duration

9 Days Duration for a 70 kg Subject at a Remodulin Dose of 30 ng/kg/min

Transition Day	Remodulin Dose (ng/kg/min)	Orenitram Dose (mg) TID
Day 1	30	0
Day 2	26	0.625
Day 3	22	1.375
Day 4	18	2
Day 5	14	2.625
Day 6	10	3.125
Day 7	6	3.75
Day 8	3	4.375
Day 9	0	5

9 Days Duration for a 40 kg Subject at a Remodulin Dose of 30 ng/kg/min

Transition Day	Remodulin Dose (ng/kg/min)	Orenitram Dose (mg) TID
Day 1	30	0
Day 2	26	0.375
Day 3	22	0.75
Day 4	18	1.125
Day 5	14	1.5
Day 6	10	2
Day 7	6	2.25
Day 8	3	2.5
Day 9	0	2.875

9 Days Duration for a 120 kg Subject at a Remodulin Dose of 30 ng/kg/min

Transition Day	Remodulin Dose (ng/kg/min)	Orenitram Dose (mg) TID
Day 1	30	0
Day 2	26	1.125
Day 3	22	2.25
Day 4	18	3.5
Day 5	14	4.625
Day 6	10	5.75
Day 7	6	6.875
Day 8	3	7.75
Day 9	0	8.625

9 Days Duration for a 70 kg Subject at a Remodulin Dose of 20 ng/kg/min

Transition Day	Remodulin Dose (ng/kg/min)	Orenitram Dose (mg) TID
Day 1	20	0
Day 2	18	0.375
Day 3	15	0.875
Day 4	13	1.125
Day 5	10	1.625
Day 6	8	2
Day 7	5	2.5
Day 8	2	3
Day 9	0	3.325

9 Days Duration for a 40 kg Subject at a Remodulin Dose of 20 ng/kg/min

Transition Day	Remodulin Dose (ng/kg/min)	Orenitram Dose (mg) TID
Day 1	20	0
Day 2	18	0.25
Day 3	15	0.5
Day 4	13	0.625
Day 5	10	1
Day 6	8	1.125
Day 7	5	1.5
Day 8	2	1.75
Day 9	0	2

9 Days Duration for a 120 kg Subject at a Remodulin Dose of 20 ng/kg/min

Transition Day	Remodulin Dose (ng/kg/min)	Orenitram Dose (mg) TID
Day 1	20	0
Day 2	18	0.625
Day 3	15	1.5
Day 4	13	2
Day 5	10	2.85
Day 6	8	3.5
Day 7	5	4.375
Day 8	2	5.125
Day 9	0	5.75

9 Days Duration for a 70 kg Subject at a Remodulin Dose of 40 ng/kg/min

Transition Day	Remodulin Dose (ng/kg/min)	Orenitram Dose (mg) TID
Day 1	40	0
Day 2	35	0.875
Day 3	30	1.625
Day 4	25	2.5
Day 5	20	3.375
Day 6	15	4.25
Day 7	10	5
Day 8	5	5.875
Day 9	0	6.75

9 Days Duration for a 40 kg Subject at a Remodulin Dose of 40 ng/kg/min

Transition Day	Remodulin Dose (ng/kg/min)	Orenitram Dose (mg) TID
Day 1	40	0
Day 2	35	0.5
Day 3	30	1
Day 4	25	1.5
Day 5	20	2
Day 6	15	2.375
Day 7	10	2.875
Day 8	5	3.375
Day 9	0	3.875

9 Days Duration for a 120 kg Subject at a Remodulin Dose of 40 ng/kg/min

Transition Day	Remodulin Dose (ng/kg/min)	Orenitram Dose (mg) TID
Day 1	40	0
Day 2	35	1.5
Day 3	30	2.875
Day 4	25	4.375
Day 5	20	5.75
Day 6	15	7.25
Day 7	10	8.625
Day 8	5	10
Day 9	0	11.5

17 Days Duration

17 Days Duration for a 70 kg Subject at a Remodulin Dose of 30 ng/kg/min

Transition Day	Remodulin Dose (ng/kg/min)	Orenitram Dose (mg) TID
Day 1	30	0
Day 3	26	0.625
Day 5	22	1.375
Day 7	18	2
Day 9	14	2.625
Day 11	10	3.125
Day 13	6	3.75
Day 15	3	4.375
Day 17	0	5

17 Day Duration for a 40 kg Subject at a Remodulin Dose of 30 ng/kg/min

Transition Day	Remodulin Dose (ng/kg/min)	Orenitram Dose (mg) TID
Day 1	30	0
Day 3	26	0.375
Day 5	22	0.75
Day 7	18	1.125
Day 9	14	1.5
Day 11	10	2
Day 13	6	2.25
Day 15	3	2.5
Day 17	0	2.875

17 Days Duration for a 120 kg Subject at a Remodulin Dose of 30 ng/kg/min

Transition Day	Remodulin Dose (ng/kg/min)	Orenitram Dose (mg) TID
Day 1	30	0
Day 3	26	1.125
Day 5	22	2.25
Day 7	18	3.5
Day 9	14	4.625
Day 11	10	5.75
Day 13	6	6.875
Day 15	3	7.75
Day 17	0	8.625

17 Days Duration for a 70 kg Subject at a Remodulin Dose of 20 ng/kg/min

Transition Day	Remodulin Dose (ng/kg/min)	Orenitram Dose (mg) TID
Day 1	20	0
Day 3	18	0.375
Day 5	15	0.875
Day 7	13	1.125
Day 9	10	1.625
Day 11	8	2
Day 13	5	2.5
Day 15	2	3
Day 17	0	3.325

17 Day Duration for a 40 kg Subject at a Remodulin Dose of 20 ng/kg/min

Transition Day	Remodulin Dose (ng/kg/min)	Orenitram Dose (mg) TID
Day 1	20	0
Day 3	18	0.25
Day 5	15	0.5
Day 7	13	0.625
Day 9	10	1
Day 11	8	1.125
Day 13	5	1.5
Day 15	2	1.75
Day 17	0	2

17 Days Duration for a 120 kg Subject at a Remodulin Dose of 20 ng/kg/min

Transition Day	Remodulin Dose (ng/kg/min)	Orenitram Dose (mg) TID
Day 1	20	0
Day 3	18	0.625
Day 5	15	1.5
Day 7	13	2
Day 9	10	2.85
Day 11	8	3.5
Day 13	5	4.375
Day 15	2	5.125
Day 17	0	5.75

17 Days Duration for a 70 kg Subject at a Remodulin Dose of 40 ng/kg/min

Transition Day	Remodulin Dose (ng/kg/min)	Orenitram Dose (mg) TID
Day 1	40	0
Day 3	35	0.875
Day 5	30	1.625
Day 7	25	2.5
Day 9	20	3.375
Day 11	15	4.25
Day 13	10	5
Day 15	5	5.875
Day 17	0	6.75

[figure not shown]
17 Days Duration for a 40 kg Subject at a Remodulin Dose of 40 ng/kg/min

Transition Day	Remodulin Dose (ng/kg/min)	Orenitram Dose (mg) TID
Day 1	40	0
Day 3	35	0.5
Day 5	30	1
Day 7	25	1.5
Day 9	20	2
Day 11	15	2.375
Day 13	10	2.875
Day 15	5	3.375
Day 17	0	3.875

17 Days Duration for a 120 kg Subject at a Remodulin Dose of 40 ng/kg/min

Transition Day	Remodulin Dose (ng/kg/min)	Orenitram Dose (mg) TID
Day 1	40	0
Day 3	35	1.5
Day 5	30	2.875
Day 7	25	4.375
Day 9	20	5.75
Day 11	15	7.25
Day 13	10	8.625
Day 15	5	10
Day 17	0	11.5

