6 DRUGS AND DOSING (OR TREATMENT PROCEDURES)

6.1 DRUG DOSAGE, ADMINISTRATION AND SCHEDULE

Remodulin will be provided in vial strengths of 1 mg/mL, 2.5 mg/mL, 5 mg/mL, and 10 mg/mL. Following completion of Baseline assessments, Remodulin will be initiated at 2 ng/kg/min SC or IV in an inpatient or outpatient setting. IV Remodulin may be administered through an indwelling central venous catheter or a peripherally inserted catheter, as clinically indicated. At the request of the Investigator, nursing support will assist subjects with initiation of SC or IV Remodulin, pump use, Remodulin dispensing, Remodulin titration, and adverse event management. If necessary, subjects can switch from IV to SC Remodulin, or SC to IV Remodulin, at the discretion of the Investigator.

Up-titration of Remodulin will continue as tolerated. Subjects should be optimized on Remodulin therapy prior to transition to Orenitram; a dose should be achieved that improves the symptoms of PAH while minimizing excessive pharmacologic effects of Remodulin. There is no maximum Remodulin dose during the study.

Subjects may transition at Weeks 2, 4, or 8 if they have achieved a minimum Remodulin dose of 20 ng/kg/min and the Investigator deems the subject suitable for transition. Subjects will transition from Remodulin to Orenitram over the course of 1 to 21 days in an inpatient or outpatient setting using a cross-taper method (ie, decreases in Remodulin dose coincide with increases in Orenitram dose). Orenitram will be provided in the extended-release tablet strengths of 0.125 mg, 0.25 mg, 1 mg, 2.5 mg, and 5 mg. Subjects will be instructed to take the appropriate number of 0.125 mg, 0.25 mg, 1 mg, 2.5 mg, and 5 mg tablets based upon their Remodulin dose and the transition schedule chosen by their healthcare provider.

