Transition may be reversed or stopped if the Investigator feels it is necessary due to significant signs or symptoms of PAH or due to serious safety concerns. If the Investigator deems a subject unsuitable for transition to Orenitram due to significant signs or symptoms of PAH or any other serious safety concerns, the subject may remain on Remodulin for the duration of the study. However, the subject should be continually assessed to determine if they become stable enough for transition to Orenitram. All subjects still on Remodulin at Week 8 should transition to Orenitram regardless of their Remodulin dose unless the Investigator deems them unsuitable for transition to Orenitram due to significant signs and symptoms of PAH or any other serious safety concerns.

Following completion of transition, Orenitram dose titration will continue in the outpatient setting through Week 16 to reach the maximum tolerated dose by increasing the dose by 0.125 mg TID every 3 to 4 days as tolerated, with the goal of achieving a maximum tolerated dose by the end of Week 16. A slower titration rate may be used if the subject experiences adverse effects. There is no maximum Orenitram dose during the study.

Orenitram will be dosed TID with food. Dosing will take place approximately every 6 to 8 hours, with adjustments permitted based on the subject's lifestyle and schedule. Study subjects should take their study drug at approximately the same times each day. Tablets must be swallowed whole and not chewed, as this will result in inappropriate delivery of the active ingredient. If the tablet is inadvertently damaged during administration, the subject/caregiver should contact site personnel to be monitored for the onset of symptoms due to possible inappropriate drug release. Subjects must not "make-up" or "double-up" on missed doses of

Orenitram. If dosing is interrupted for longer than 24 hours, consideration should be given to gradually re-titrating the subject's dose to the last dose administered prior to the dose interruption, particularly in cases where the last dose prior to interruption was greater than 3 mg.

In the event of a planned short-term treatment interruption for subjects unable to take oral medications after beginning transition to Orenitram, consider a temporary infusion of SC or IV Remodulin using the following equation to calculate the dose of Remodulin:

Remodulin (ng/kg/min) =
$$(139 \times \text{Orenitram TDD [mg]}) \div \text{weight (kg)}$$

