7.3.4 Transition Visit (Week 2, 4, or 8)

Subjects may transition at Weeks 2, 4, or 8 if they have achieved a minimum Remodulin dose of 20 ng/kg/min and the Investigator deems the subject suitable for transition. Subjects will transition from Remodulin to Orenitram over the course of 1 to 21 days in an inpatient or outpatient setting using a cross-taper method (ie, decreases in Remodulin dose coincide with increases in Orenitram dose). Subjects will be instructed to take the appropriate number of Orenitram tablets based upon their Remodulin dose and the transition schedule chosen by their healthcare provider.

At the discretion of the Investigator, transition may also be reversed or stopped if necessary due to significant signs or symptoms of PAH or due to serious safety concerns. If the Investigator deems a subject unsuitable for transition to Orenitram due to significant signs and symptoms of PAH or any other serious safety concerns, the subject may remain on Remodulin for the duration of the study. However, the subject should be continually assessed to determine if they become stable enough for transition to Orenitram. All subjects still on Remodulin at Week 8 should transition to Orenitram at Week 8 regardless of their Remodulin dose unless the Investigator deems them unsuitable for transition to Orenitram due to significant signs and symptoms of PAH or any other serious safety concerns.

Transition will occur as follows:

- The dose of Remodulin can be reduced no more than 10 ng/kg/min per day for transitions in the outpatient setting. For inpatient transitions, there is no limit on the rate of Remodulin dose reduction.
- The target dose of Orenitram at the end of transition is dependent on the subject's weight and Remodulin dose. Up-titration of Orenitram should coincide with a reduction in the Remodulin dose. The target TDD of Orenitram at the end of

transition will be calculated based upon the following equivalence weight-based formula:

TDD [mg] = 0.0072 * Remodulin dose [ng/kg/min] * weight [kg].

- The Orenitram up-titration dose should be taken at approximately the same time the Remodulin dose is decreased.
- Examples of transition schedules for various subject body weights and Remodulin doses are listed in Appendix I.

The following subject-reported data will be completed by the subject at the Transition Visit prior to all other assessments and prior to initiation of Orenitram: emPHasis-10 questionnaire and TSQM.

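### The 3-day, 70 kg, 20 ng/kg/min example schedule in Appendix I ends at 1 mg per dose, 29.8% of the 3.36 mg that the protocol's own equation gives

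*Protocol*

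**What the plan says.** Protocol Section 7.3.4 sets the target Orenitram total daily dose (TDD) at the end of transition by an equation: "TDD [mg] = 0.0072 * Remodulin dose [ng/kg/min] * weight [kg"]. It then points to the appendix: "Examples of transition schedules for various subject body weights and Remodulin doses are listed in Appendix I". Under Section 6.1, subjects take tablets according to their Remodulin dose and "the transition schedule chosen by their healthcare provider". After transition the dose rises by "increasing the dose by 0.125 mg TID every 3 to 4 days as tolerated".

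Appendix I has 36 schedules: 3, 5, 9 and 17 days, for 40, 70 and 120 kg, at 20, 30 and 40 ng/kg/min. The table headed "3 Days Duration for a 70 kg Subject at a Remodulin Dose of 20 ng/kg/min" steps Remodulin through 20, 18, 15, 13, 10, 8, 5, 2, 0. Beside these, Orenitram rises in even 0.125 mg steps from 0 to 1 mg. Three other tables cover the same weight and Remodulin dose:

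- "5 Days Duration for a 70 kg Subject at a Remodulin Dose of 20 ng/kg/min" ends at 3.375 mg.
- "9 Days Duration for a 70 kg Subject at a Remodulin Dose of 20 ng/kg/min" ends at 3.325 mg.
- "17 Days Duration for a 70 kg Subject at a Remodulin Dose of 20 ng/kg/min" ends at 3.325 mg.

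**The concern.** The four tables for this subject should end at the same dose, because the target depends on weight and Remodulin dose and not on the length of the taper. One of them ends at less than a third of the others. It also ends at half the 2 mg shown for a 40 kg subject on the 3-day schedule at the same Remodulin dose, although the target rises with weight.

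Two things are at stake. The first is safety: a cross-taper is meant to hold treprostinil exposure roughly level, and this one withdraws most of it in 3 days. The second is the primary endpoint. A subject who starts the Orenitram phase at 1 mg TID has far to climb to 4 mg TID by Week 16, so a table error could be counted as failure to achieve the dose.

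The combination is an easy one to pick. The dose of 20 ng/kg/min is the minimum for elective transition, and 70 kg is the weight used for the dose equivalences in Section 1.3 and the weight cut-off in the primary endpoint. The Remodulin steps also respect the outpatient limit of 10 ng/kg/min per day.

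**Working it through.** **Inputs.** Forward equation: Section 7.3.4. Reverse equation, Remodulin = 139 × TDD ÷ weight, and TID dosing: Section 6.1. Visit days (15, 29, 57, 113) and windows: Section 3.1. Doses: Appendix I.

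**End dose.** The equation gives 0.0072 × 20 × 70 = 10.08 mg/day, and 10.08 ÷ 3 = 3.36 mg per dose. The nearest 0.125 mg multiple is 3.375 mg, which reproduces the 5-day table. The 3-day figure of 1 mg is not reproduced: 1 ÷ 3.36 = 0.298.

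**Other schedules.** The same calculation on the final row of each of the other 35 schedules gives printed-to-equation ratios from 0.990 (9- and 17-day, 70 kg, 20 ng/kg/min) to 1.042 (40 kg, 20 ng/kg/min).

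**Remodulin equivalent of the end dose.** 139 × 3 ÷ 70 = 5.96 ng/kg/min. Inverting the forward equation gives 3 ÷ (0.0072 × 70) = 5.95.

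**Nominal combined exposure by row**, as Remodulin + 139 × (3 × Orenitram dose) ÷ 70. This treats each row's single dose as if taken three times that day:

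| Remodulin (ng/kg/min) | Orenitram printed (mg) | Combined | Orenitram corrected (mg) | Combined |
|---|---|---|---|---|
| 20 | 0 | 20.0 | 0 | 20.0 |
| 18 | 0.125 | 18.7 | 0.375 | 20.2 |
| 15 | 0.25 | 16.5 | 0.875 | 20.2 |
| 13 | 0.375 | 15.2 | 1.125 | 19.7 |
| 10 | 0.5 | 13.0 | 1.625 | 19.7 |
| 8 | 0.625 | 11.7 | 2 | 19.9 |
| 5 | 0.75 | 9.5 | 2.5 | 19.9 |
| 2 | 0.875 | 7.2 | 3 | 19.9 |
| 0 | 1 | 6.0 | 3.375 | 20.1 |

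**Reach by Week 16.** Assume that transition starts on the nominal visit day, that its last day is 2 days later, and that one 0.125 mg TID step then follows every 4 or every 3 days to Day 113.

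| Transition visit | Days left | Steps (every 4 / every 3 days) | From 1 mg (mg TID) |
|---|---|---|---|
| Week 2 | 113 − 17 = 96 | 24 / 32 | 4.0 to 5.0 |
| Week 4 | 113 − 31 = 82 | 20 / 27 | 3.5 to 4.375 |
| Week 8 | 113 − 59 = 54 | 13 / 18 | 2.625 to 3.25 |

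With the most favourable visit windows after Week 8, the time left is Day 120 − Day 54 = 66 days, or 22 three-day steps. The dose is then 1 + 22 × 0.125 = 3.75 mg TID, or 11.25 mg/day, still below 12. From the correct 3.375 mg, a nominal Week 8 transition reaches 3.375 + 13 × 0.125 = 5.0 to 3.375 + 18 × 0.125 = 5.625 mg TID.

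**Weight of one subject.** 1 ÷ 30 = 3.3 percentage points with the protocol's sample size, or 1 ÷ 35 = 2.9 with the SAP's.

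**The case against.** The strongest reply is that the rule is right and binding. Section 7.3.4 requires the target to be calculated, and the appendix only illustrates it. Section 6.1 does not name Appendix I or waive the calculation, so a site that stops at 1 mg TID has skipped a step. The case is also narrow: one schedule of 36, a subject near 70 kg at the minimum dose, and a 3-day taper when 1 to 21 days are allowed. Sites contact the subject daily during transition and may reverse or stop it. All of this stands, and it makes the harm conditional. It does not make the table right. Daily contact also drops to twice weekly once Remodulin stops, which is when the full deficit begins.

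Some smaller points also stand:

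- The row-by-row exposures are nominal. Actual Orenitram intake on Day 3 of the table is 0.75 + 0.875 + 1 = 2.625 mg. The direction is not in doubt.
- Final rows do not test every entry. In the 3-, 9- and 17-day tables for 70 kg at 30 ng/kg/min, the doses at Remodulin 10 and 6 are 3.125 and 3.75 mg, about 7% below the 3.36 and 4.03 mg implied by the Remodulin removed. Those tables still end at the right dose, so this is a different and minor matter.
- The endpoint consequence assumes that nobody notices the low dose and corrects it to the calculated target.

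A text-extraction fault is not a plausible explanation, because the whole column is a regular 0.125 mg ladder. Reading 1 mg as a daily total would only widen the gap.

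**Conclusion.** The concern holds. The end dose is 3 mg/day against 10.08 mg/day, a shortfall of about 70%, and no other schedule in Appendix I has a comparable final-dose error.

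The arithmetic rests only on the protocol's own equations. The consequences rest on two conditions: a site uses the table without checking the equation, and the low dose is then left to routine titration. Under those conditions, the primary endpoint is just reachable after a Week 2 transition, depends on titration speed after Week 4, and is out of reach after Week 8. The documents do not show whether any subject was transitioned on this table, so the probability of harm is unknown. A dosing table this far from its governing equation, at the minimum transition dose and the protocol's reference weight, should still be corrected on patient-safety grounds.

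**What to change.** Replace the Orenitram column of this table with 0, 0.375, 0.875, 1.125, 1.625, 2, 2.5, 3, 3.375 mg. These are the 9-day values for the same Remodulin steps, with the last entry rounded to a dispensable dose. Notify sites.

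Editorial, on the same pages: several entries are not multiples of 0.125 mg. Change 3.325 to 3.375, 2.85 to 2.875 and 0.675 to 0.625. The entry 2.675 can go to 2.625 or 2.75, since the equation gives 0.0024 × 28 × 40 = 2.688, essentially midway.

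Optional: use the dose listings and transition durations planned in SAP Section 3.3.7 to look for subjects who may have followed the uncorrected table. Those outputs do not record which table was used, so confirm from site dosing records. Otherwise subjects would be picked out by their low dose, which would preferentially remove endpoint failures. If any are confirmed, show the primary percentage with and without them, keeping the full result as primary.

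The cost is one corrected column, a few rounded entries and a site notice, with no extra patients or procedures.
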